8.2. Primary Safety Endpoint

The safety endpoint will be analyzed using the modified Intent-to-Treat population (mITT population) as defined in Section 3.

Serious adverse events through 30 days as indicated below:

- Serious intraoperative and post-operative complications between each cohort
- Device-related serious adverse events (SAEs)

8.2.1. Primary Safety Endpoint Analysis

By the occurrence or proportion of the serious complication, and the serious adverse device event (ADE) among study subjects within each HPI arm, a two-sample t-test for proportions will be used for the statistical comparison.

$$t = \frac{\widehat{p}_1 - \widehat{p}_0}{\sqrt{\widehat{p}_{pool} * (1 - \widehat{p}_{pool}) \left(\frac{1}{n_1} + \frac{1}{n_0} \right)}}$$

Here \widehat{p}_1 , \widehat{p}_0 are the complication, and serious ADE occurrence proportion as the estimates of population occurrence probability of HPI arm ($\widehat{p}_1 = \frac{x_1}{n_1}$) and control group ($\widehat{p}_0 = \frac{x_0}{n_0}$) respectively, \widehat{p}_{pool} is the pooled event occurrence probability derived with following algorithm $\widehat{p}_{pool} = \frac{x_0 + x_1}{n_0 + n_1}$, n_1, n_0 is the final valid subjects in HPI arm and control group respectively, x_1, x_0 is the events (AE) recorded in study subjects of HPI arm and control group respectively. If the p value from this analysis is less than 0.025 and the proportion difference in t statistic calculation is negative, it is the expected result. Following conclusion will be drawn that the application of HPI software system can statistically decrease the complications and SAE occurrence.

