THIS DOCUMENT CONTAINS CONFIDENTIAL AND PROPRIETARY INFORMATION OF EDWARDS LIFESCIENCES, LLC. IT MAY NOT BE REPRODUCED OR DISCLOSED WITHOUT PRIOR WRITTEN PERMISSION FROM EDWARDS LIFESCIENCES, LLC.

Edwards Lifesciences, Edwards, the stylized E logo, HemoSphere, Acumen IQ, Swan Ganz and ForeSight Elite are trademarks of Edwards Lifesciences Corporation.

The primary safety endpoints are serious adverse events through 30 days as indicated below:

- Serious intraoperative and post-operative complications
- Device-related serious adverse events and adverse events

The exploratory evaluations are indicated below:

- Subgroup analysis of primary and secondary endpoints by age stratification
- Subgroup analysis of primary and secondary endpoints by gender
- Subgroup analysis of primary and secondary endpoints by race
- Protocol adherence to HPI alert, as defined by >50% HPI alerts with documented intervention per the suggested treatment algorithm within a 5 minute timeframe
- Difference in time spent in hypertension defined as TWA of MAP>110, >120 and >130 mmHg post-cardiopulmonary bypass CPB) through the first 8-hour ICU period as compared with the control group.
- In-hospital mortality rate
- Incidence of cerebral desaturations defined as total time below 10% relative to baseline NIRS values.
- Percent of monitoring time with CO or CI within 10% relative to pre-induction baseline
- ICU Length of Stay
- Hospital Length of Stay
- Time to extubation
- SOFA scores
- New onset atrial fibrillation, detected prior to ICU discharge

THIS DOCUMENT CONTAINS CONFIDENTIAL AND PROPRIETARY INFORMATION OF EDWARDS LIFESCIENCES, LLC. IT MAY NOT BE REPRODUCED OR DISCLOSED WITHOUT PRIOR WRITTEN PERMISSION FROM EDWARDS LIFESCIENCES, LLC.

Edwards Lifesciences, Edwards, the stylized E logo, HemoSphere, Acumen IQ, Swan Ganz and ForeSight Elite are trademarks of Edwards Lifesciences Corporation.

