7. STATISTICAL METHODS

Statistical Analysis Plan (SAP)

There will be a formal SAP, separate from this HPI CARE Trial protocol. The formal SAP will be completed prior to database lock and the analysis of any HPI CARE Trial endpoints data. The SAP will detail the planned statistical analyses. The subsections below summarize the planned analyses.

Primary Effectiveness Endpoint

The primary objective of this trial is to determine whether the use of the Acumen™ HPI Feature Software to guide hemodynamic management in critically ill patients in the cardiac operating room (OR) and the cardiovascular intensive care unit (CVICU) reduces the duration (t[mins]) of hypotension below a threshold of Mean Arterial Pressure (MAP), defined as MAP <65mmHg.

Sample Size Justification

In the HPI CARE Trial, the reduction of the mean duration of hypotension in the operating room (OR) and intensive care unit (ICU), is the primary endpoint. The following statistical hypotheses are designed and used for the sample size estimation.

$$H_n: \mu_1 \geq \mu_0$$

$$H_a: \mu_1 < \mu_0$$

where μ_1, μ_0 are the mean hypotension duration of the test arm and reference arm, respectively.

Because there are no publications available targeting hypotension management in the ICU, the sample size estimation is conducted based on the summary statistics from OR measurement. By the summary statistics (mean and standard deviation) of hypotension duration from post-CPB and closed chest ^[3,5], the following statistics are calculated and applied in sample size estimation: hypotension mean=29 (minutes), standard deviation=29.4 (minutes).

By clinical study design, type I error $\alpha = 0.025$ (one side test), test power= $(1 - \beta) = 0.80$, the expected hypotension duration reduction rate by HPI software and the treatment protocol is 30%, the expected ratio of hypotension duration standard deviation divided by the mean hypotension in the test arm will be 1.10 (obtained from a previous non-cardiac OR HPI study, Edwards Lifesciences), with SAS PROC POWER, the estimate of sample size is 171 per group. β is type II error.

Primary Safety Endpoint

The primary safety endpoint is to assess all serious intraoperative and post-operative adverse events through 30 days, including serious device-related events.

Analysis Populations

A. mITT population

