8.3. Multiplicity Adjustment

The family-wise Type I error rate between the primary efficacy and safety endpoints will be controlled using a hierarchical gatekeeping method. If the primary efficacy endpoint is not passed, then the safety endpoints will not be tested either. If the primary endpoint is passed, then the secondary endpoints will be tested using a one-sided α at the same level as the primary endpoint.

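### SAP 8.2.1 does not say whether the primary safety test is one composite or two component tests, and SAP 8.3 sets no order, split or pass rule among the safety endpoints it claims to control.

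*Combined protocol and SAP*

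**What the plan says.** **Definition of the endpoint.** Protocol section 7 (Primary Safety Endpoint) describes a single overall endpoint: "The primary safety endpoint is to assess all serious intraoperative and post-operative adverse events through 30 days, including serious device-related events". The protocol synopsis, SAP 3.2 and SAP 8.2 list two items, the first being "Serious intraoperative and post-operative complications between each cohort" and the second device-related SAEs. Protocol section 3 speaks of endpoints in the plural, and its second item is wider: "Device-related serious adverse events and adverse events", which brings in non-serious device events.

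**Test.** SAP 8.2.1 names both components, "By the occurrence or proportion of the serious complication, and the serious adverse device event (ADE) among study subjects within each HPI arm", and gives one pooled-proportion statistic referred to t. The numerator x "is the events (AE) recorded in study subjects of HPI arm and control group respectively", so it counts events rather than subjects. The decision rule reads "If the p value from this analysis is less than 0.025 and the proportion difference in t statistic calculation is negative", and the conclusion is that the HPI system "can statistically decrease the complications and SAE occurrence". The section does not say whether p is one- or two-sided.

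**Multiplicity.** SAP 8.3 places safety behind efficacy: "If the primary efficacy endpoint is not passed, then the safety endpoints will not be tested either". It says family-wise error between efficacy and safety is controlled, and gives no order, alpha split or pass rule within safety.

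**Precedence.** The SAP introduction says the SAP governs where study documents conflict on data analysis, so the single endpoint in protocol section 7 cannot be relied on to settle the matter.

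**The concern.** This is a primary endpoint that carries a superiority claim, so the contrast has to be fixed before anyone sees the data. As written, three readings are open: one composite, two tests with either sufficient, or two tests with both required. They can disagree on the same data. Suppose serious complications are clearly fewer in the HPI arm and no device-related SAE occurs in either arm. The composite passes, the either-passes rule passes, and the both-must-pass rule cannot pass because the device statistic does not exist.

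Under the either-passes rule the family-wise control stated in SAP 8.3 does not extend to the two safety tests, because nothing shares the 0.025 between them.

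**Working it through.** **Inputs.** Threshold 0.025 with a negative difference required (SAP 8.2.1). 175 subjects per group (SAP 8.1.4). The documents give no safety event rate, so the rates below are assumptions: 20% for serious complications and 0.1% to 2% for device-related SAEs, equal in both arms.

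**1. The plan's own figure.** The 0.025 is declared, not derived. Exact binomial enumeration of the SAP 8.2.1 pooled statistic (175 per arm, one-sided t reference, 348 df) gives a size of 0.0246 to 0.0248 at event rates of 10% to 30%. A single contrast with reasonably common events therefore runs at about its nominal level.

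**2. Error by reading, both tests at full size.**
- One composite, or both must pass: at most 0.025.
- Either passes, one-sided: upper bound 0.025 + 0.025 = 0.050. If independent, 1 − (1 − 0.025)² = 0.0494. For bivariate normal statistics with correlation 0.3, 0.5 and 0.8, the error is 0.0476, 0.0454 and 0.0390.
- Either passes, with 0.025 a two-sided p plus the direction condition: 0.0125 per test, total at most 0.025.

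**3. Sparse device events.** The device test does not run at full size when events are rare. With no HPI-arm events, 3 control events give t = −1.74 (no rejection). Four give a pooled proportion of 4/350 = 0.01143 and t = −(4/175)/√(0.01143 × 0.98857 × 2/175) = −2.01. The one-sided p is then 0.0225 and the two-sided p 0.0450, so sidedness alone changes this result. With 1 HPI event, 7 control events are needed.

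The chance of no device event in either arm is (1 − rate)^350. The combined either-passes error is 1 − (1 − 0.0247)(1 − device-test size), where 0.0247 is the exact size for complications at 20% and the components are taken as independent.

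| Assumed device-SAE rate | Device-test size | Statistic is 0/0 | Combined error |
|---|---|---|---|
| 0.1% | 0.00003 | 70% | 0.0247 |
| 0.2% | 0.0003 | 50% | 0.025 |
| 0.25% | 0.0007 | 42% | 0.0254 |
| 0.5% | 0.0050 | 17% | 0.0296 |
| 1% | 0.0178 | 3% | 0.0421 |
| 2% | 0.0225 | 0.1% | 0.0467 |

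Moving the complication rate to 10% or 30% changes the combined error by no more than about 0.0002.

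**4. Numerator.** With x counting events, a subject with several events contributes several times. The quantity x/n can exceed 1, and if the pooled value exceeds 1 the term under the square root is negative. A count of subjects with at least one event cannot do this.

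**The case against.** The strongest reply is that SAP 8.2.1 reads most naturally as one test. It has one formula, one p value and one joint conclusion, and SAP 8.2 speaks of the safety endpoint in the singular. No sentence says that passing on one component is enough. A composite or both-must-pass reading fits that text and does not inflate error. This stands, and it makes the either-passes reading a possibility left open, not the plan's stated rule. It does not remove the gap: SAP 8.3 uses the plural, the section names two components, and nothing says they are pooled.

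A reader might infer three stronger things that the documents do not support.

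- **That the safety error doubles.** This needs two separate tests, an either-passes rule, a one-sided p, an efficacy gate already open, and device-related SAEs at roughly 1% to 2% or more. If HPI has no effect on hypotension, a false safety claim also requires a false efficacy pass.
- **That the device test is uncomputable by design.** All subjects wear the sensor, including controls (protocol section 6, Procedure), so control-arm events can occur. The statistic is 0/0 only when neither arm has an event, and no reduction could be claimed then anyway. Rates low enough to make 0/0 common are also rates at which the device test adds almost no error, so the two problems do not arise together.
- **That the protocol says one endpoint and the SAP says two.** Only protocol section 7 describes a single endpoint. The synopsis and section 3 list two items, so the conflict lies inside the protocol as well.

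Descriptive reporting of device events is also partly planned already: SAP 9.2 tabulates ADEs, SAEs and SADEs by arm, and SAP 9.4 gives relative risks with 95% intervals for AEs and SAEs.

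**Conclusion.** The point holds as a failure to define the primary safety contrast, made worse by conflicting endpoint definitions. Its effect on error depends on a choice that the SAP does not make, and 0.05 is a ceiling, not an expected value. The intermediate figures rest on equal event rates in the two arms, independent components and assumed device-SAE rates. The risk section of the protocol does not expect the sensor to add risk, but it does list harms from under- or overtreatment under the treatment protocol, so neither end of the assumed range can be excluded.

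The more certain harm is that the rule could be chosen after the data are seen. This should be corrected before database lock. It does not threaten the primary efficacy analysis.

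**What to change.** In SAP 3.2 and 8.2.1, name one primary safety contrast: the proportion of subjects with at least one SAE through day 30, HPI minus control, tested at one-sided 0.025. Protocol section 7 points towards a single overall endpoint but does not itself specify a subject-level proportion or the direction of the difference, so the SAP has to state both. This also replaces the event-count numerator.

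Report device-related SAEs and AEs by arm as counts with exact intervals and no formal test. If both components must be tested, fix their order in SAP 8.3 (or split alpha, one-sided 0.0125 each) and use an exact method for device-related events.

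Reconcile the protocol synopsis, protocol sections 3 and 7, and SAP 3.2, 8.2 and 8.2.1, including whether non-serious device-related AEs belong to the endpoint.

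No new data are needed. The change is SAP wording, plus alignment of the protocol text. The downside is that device-related SAEs lose a formal p-value, which at low event rates would carry little information.

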8.3. Multiplicity Adjustment

The family-wise Type I error rate between the primary efficacy and safety endpoints will be controlled using a hierarchical gatekeeping method. If the primary efficacy endpoint is not passed, then the safety endpoints will not be tested either. If the primary endpoint is passed, then the secondary endpoints will be tested using a one-sided α at the same level as the primary endpoint.

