8.1.4. Interim Analysis

To monitor the effectiveness and safety of HPI software on hypotension management in cardiac surgery and ICU for study patient requiring cardiac pulmonary bypass, one interim analysis is planned and will be conducted at the time that half of the enrolled study subjects' complete surgery and the hemodynamic measurements are downloaded from the monitoring platform.

To compensate for the early look at the data during the interim analysis, using the Pocock methodology, for this study design, 11~12% extra study subjects will be enrolled. Considering drop-out through withdraw ICF, lost follow-up, and roll-in subjects for training et al, another 10% attrition is added for subject enrollment, considering the study subject randomization, the final sample size is 175 subjects per group.

This interim analysis focuses on the primary effectiveness endpoint, the subject total hypotension duration during post-cardiac pulmonary bypass stage and the first 8 hours for patients in intensive care unit. The reduction of mean hypotension duration between the HPI arm and control group will be tested by t (student) statistics with $n_1 + n_2 - 2$ degree of freedom. If the corresponding p value of this t statistics is less than the critical p value=0.0154 (the type I error allocation by the study design) together with the mean hypotension

 Edwards	Revision Date: May 7, 2024	Rev	For Use Only by Affiliates of Edwards Lifesciences	Page 16
	Title	A randomized trial of the Hypotension Prediction Index in the cardiac operating room and the intensive care unit		

minutes of HPI arm study subject is smaller than the number of control group study subject, the null hypothesis is rejected. By this interim analysis result, the study team will make a decision whether stop the clinical study or continue until the maximum study subjects are enrolled and the study is completed.

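### The formal primary safety test runs only if efficacy passes, has a written conclusion only for benefit, and counts events where its formula needs subjects

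*Combined protocol and SAP*

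**What the plan says.** Four places bear on the point.

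- **SAP 8.3 (Multiplicity Adjustment)** states the aim: "The family-wise Type I error rate between the primary efficacy and safety endpoints will be controlled using a hierarchical gatekeeping method". It then sets the rule: "If the primary efficacy endpoint is not passed, then the safety endpoints will not be tested either".
- **SAP 8.2.1 (Primary Safety Endpoint Analysis)** gives the decision rule, "If the p value from this analysis is less than 0.025 and the proportion difference in t statistic calculation is negative", and the only conclusion that follows from it, that "the application of HPI software system can statistically decrease the complications and SAE occurrence". It does not say how a positive difference would be read, or whether the p-value is one- or two-sided.
- **SAP 8.2.1 on the statistic** is inconsistent. The text speaks of a proportion "among study subjects within each HPI arm, a two-sample t-test for proportions will be used for the statistical comparison", and the formula uses the pooled binomial variance. The numerator (x1 and x0), however, "is the events (AE) recorded in study subjects of HPI arm and control group respectively".
- **SAP 8.1.4 (Interim Analysis)** gives monitoring of effectiveness and safety as the purpose of the interim, then says: "This interim analysis focuses on the primary effectiveness endpoint". It lists no safety output.

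Outside the formal test, SAP 9.1, 9.2 and 9.4 call for deaths and adverse events by arm in the mITT population, and for relative risks of AEs and SAEs with 95% confidence intervals. None of these depends on efficacy.

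**The concern.** A primary safety endpoint is there chiefly to find out whether the intervention does harm. Protocol section 8 says the HPI treatment protocol may lead to under- or overtreatment, and lists heart failure, cardiac ischemia and tachyarrhythmia among the possible results. The formal test does not serve that purpose, for three reasons.

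- It is withheld when efficacy fails. In that case there is no benefit to weigh against any excess of events.
- When it is run, an excess on HPI has no pre-specified reading.
- If the numerator is taken literally, the error rate for the one permitted claim, that HPI reduces complications and SAEs, is not the stated one.

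The risk is a favourable safety claim made at an inflated error rate, or an excess left to be interpreted after the data are seen.

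**Working it through.** **Inputs.** SAP 2.4.3: one-sided alpha 0.025, power 0.80, means 29 and 20.3 minutes, SDs 29.49 and 22.33, 142 per arm, 157 after 10% attrition. SAP 8.2.1: threshold 0.025 with a negative difference. The documents give no SAE rate, no events per subject and no power for safety, so every event rate below is an assumption and is shown as a range.

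**1. The plan's own figure.** n = (29.49² + 22.33²)(1.960 + 0.842)² / 8.7² = 1368.3 × 7.85 / 75.7 ≈ 142 per arm, which reproduces. This sizes efficacy only. There is no corresponding safety calculation to reproduce.

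**2. How often the gate closes.** On those design values, and ignoring the interim, the formal safety test is withheld in 1 − 0.80 = 20% of trials at the planned effect. If HPI has no effect on hypotension, it is withheld in 1 − 0.025 = 97.5%.

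**3. What the formula needs.** The statistic is (x1/n1 − x0/n0) / √[p(1−p)(1/n1 + 1/n0)], with p the pooled x/n. Let each subject contribute a count with mean m. A whole-number count has mean square at least m, with equality only if it is always 0 or 1. Its variance is therefore at least m − m² = m(1−m), and strictly larger once any subject can have two events. The formula then understates the variance.

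**4. Size of the error.** The large-sample one-sided error is 1 − Φ(1.96 √[m(1−m)/V]), where V is the true per-subject variance. Sample size cancels.

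- Poisson: V = m. At m = 0.2 this is 1 − Φ(1.96√0.8) = 1 − Φ(1.753) = 0.040. At m = 0.4 it is 1 − Φ(1.96√0.6) = 1 − Φ(1.518) = 0.065.
- Negative binomial, k = 0.5: V = m(1 + 2m). At m = 0.2 it is 1 − Φ(1.96√(0.8/1.4)) = 1 − Φ(1.482) = 0.069. At m = 0.4 it is 1 − Φ(1.96√(0.6/1.8)) = 1 − Φ(1.132) = 0.129.

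Simulation of the SAP statistic with no arm difference, 157 per arm:

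| Events per subject (assumed) | Poisson | Neg. binomial, k = 0.5 |
|---|---|---|
| 0.02 | 0.024 | 0.026 |
| 0.05 | 0.027 | 0.033 |
| 0.1 | 0.031 | 0.045 |
| 0.2 | 0.040 | 0.069 |
| 0.4 | 0.065 | 0.129 |

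At a mean of 1.0 the pooled p reaches 1 or more in about half of trials. The square root is then zero or of a negative number, and no statistic exists. If the SAP's p is two-sided, the nominal benefit-side rate is 0.0125, and the values at 0.2 events per subject are about 0.023 and 0.045. The relative inflation is similar or larger.

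**5. If x counts subjects with at least one event.** With true risks of 10% to 50%, the simulated error is 0.024 to 0.026. The test holds its level.

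**6. What happens under harm.** Suppose HPI raises the risk from 20% to 30% (assumed). The only written conclusion, benefit, is reached with probability about 0.00003. Observed counts of 47/157 against 31/157 would give a statistic of 0.102/0.0488 = 2.09, to which 8.2.1 attaches no reading.

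**The case against.** The strongest reply has four parts.

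**Gating a superiority claim is ordinary practice.** Test 8.2.1 as written is a claim that HPI lowers complications, and placing it behind efficacy controls family-wise error, which is the purpose 8.3 states. This stands for that claim. The 20% and 97.5% above therefore count trials in which the formal test is withheld, not trials in which safety data go uncompared. It does not explain why the only formal comparison for a primary safety endpoint should be this claim.

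**The trial is not silent on safety.** A reader might infer from 8.3 that a trial failing on efficacy would report no safety comparison, or that the plan cannot show harm. The documents do not support that. The outputs in SAP 9.1, 9.2 and 9.4 are ungated, and the example above would appear in the 9.4 plots as a relative risk of 1.52 (95% CI 1.02 to 2.25). SAP 8.4.2 also gives clinical endpoint rates by arm. Section 8.3 says the safety endpoints are not tested; it does not say they are not reported.

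**The numerator may be loose wording.** A reader might also conclude that the p-value is simply invalid. The references to a proportion and to study subjects, and the binomial variance, all point to a subject-level count, and on that reading the test is sound. This stands as a limit: the fault is a definition that contradicts its own formula, and the inflation applies only if the definition is programmed as written. At low event rates it is negligible.

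**The interim is not the only safeguard.** Section 8.1.4 says the interim focuses on effectiveness, which does not exclude a look at safety. The independent Medical Reviewer adjudicates all adverse events (protocol section 10), and the sponsor must suspend the trial on suspected unacceptable risk (protocol section 20). So the interim gap is secondary. But the role described is event-by-event adjudication, and no by-arm comparison is specified at that look.

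**Conclusion.** Wrong as written, within a limited scope: the formal primary safety analysis in SAP 8.2.1 and 8.3. The gate and the benefit-only conclusion are plain in the text and rest on no assumption.

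The numerator problem is conditional. Read literally, the one-sided error exceeds 0.025 whenever subjects can have more than one event. It is about 4% (Poisson) to 7% (negative binomial, k = 0.5) at 0.2 events per subject, 6% to 13% at 0.4, and close to nominal at 0.02 to 0.05. These figures assume 157 per arm, a one-sided p-value, and event rates and dispersion that the documents do not supply. If x is the number of subjects with an event, the test holds its level.

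The section 9 displays mean harm can be seen. They do not give the primary safety endpoint a defined reading when events are in excess on HPI.

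**What to change.** - **SAP 8.2.1:** define x1 and x0 as the number of subjects with at least one qualifying event. State whether the p-value is one- or two-sided.
- **SAP 8.3:** take the primary safety endpoint out of the efficacy gate. Keep the gate only for a claim that HPI reduces SAEs.
- **Reporting:** give the risk difference (HPI minus control) with a two-sided 95% confidence interval whatever the efficacy result, and state how an excess will be read. Use an exact method for device-related SAEs, which may be sparse; with none in either arm the present statistic is 0/0. The particular interval and exact test are a matter of choice.
- **SAP 8.1.4:** since the interim is said to monitor safety, add the existing by-arm SAE table to its output.

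The cost is SAP wording and one table already planned for the final analysis, with no new data. The repaired comparison would still have limited power for harm. At 157 per arm and one-sided 0.025 it is about 27% for 10% against 15% and 54% for 20% against 30% (assumed risks), so an interval that includes zero should not be read as evidence of no harm.
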